8.2. Summary of Nonclinical Studies

Nonclinical studies necessary to support clinical studies have been performed and are summarized in the Investigator Brochure (IB) (Endo, 2017). Nonclinical studies in the following areas were performed: toxicology, reprotoxicity, genotoxicity, and hypersensitivity.

8.3. Summary of Known Risks and Benefits

A summary of safety risks is provided in the IB (Endo, 2017). The following AEs have been commonly observed: local injection site reactions (including injection site bruising, injection site swelling, and injection site pain) for the various approved indications as well as those being investigated.

In the Phase 2b study of CCH in women with EFP, the following treatment related AEs were reported $\geq 2\%$ of 189 CCH-treated female subjects: injection site bruising (75.1%), injection site pain (59.3%), injection site nodule (14.3%), injection site pruritus (11.1%), injection site swelling (7.4%), injection site induration (5.8%), injection site mass (5.3%), injection site

discoloration (3.2%), and injection site erythema (2.1%). These events are similar to events reported in the clinical trials of EN3835 for the approved indications.

Postmarketing safety data are consistent with safety data reported in clinical trials. AEs reported to date in ongoing Phase 3 trials of CCH for the treatment of EFP of the buttocks have not indicated any new safety signals.

8.4. Rationale

The results from the Phase 2b EFP study (EN3835-201) further suggested that CCH 0.84 mg per treatment area (quadrant) is an effective treatment of EFP based on improvement in the severity of cellulite as determined by the Investigator and the subject. There were no safety concerns following 0.84 mg per treatment area in the treatment of EFP. Safety findings from the Phase 2b EFP and ongoing Phase 3 studies are similar to that observed in previous clinical studies with CCH in the treatment of EFP and XIAFLEX in the treatment of Dupuytren's contracture and Peyronie's disease, in that the majority of AEs occurred at the site of injection and resolved before the next scheduled treatment. The immunogenicity profile of CCH in the Phase 2b EFP study is similar in previous studies and programs.

Input from published literature, as well as input from aesthetic medicine specialists, indicated a desire to investigate multiple injection/dosing techniques of CCH for EFP treatment and to examine the role 3-dimensional (3-D) imaging paradigms can play in visualizing the treatment effect of CCH on EFP.

This clinical study protocol will explore these different treatment and outcome assessment paradigm possibilities. Learnings from this study could assist both the sponsor and the aesthetic medicine community in designing future clinical studies.

9. OBJECTIVES

9.1. Primary Objective

The primary objective of this study is to assess the treatment effects of CCH when administered by different injection techniques in subjects with EFP.

9.2. Secondary Objective

The secondary objective of this study is to assess the safety of CCH when administered using different injection techniques in subjects with EFP.

9.3. Exploratory Objectives

The exploratory objectives of this study include:

- To assess the immunogenicity of CCH in the treatment of EFP.
- To assess the usefulness of 3-D photography in evaluating outcomes of treatment for EFP.

10. INVESTIGATIONAL PLAN

10.1. Study Design

This is a Phase 2a, open-label, multicenter, exploratory study to evaluate the safety and effectiveness of different injection techniques of CCH for the treatment of adult women with mild, moderate or severe EFP (as assessed by the investigator using the CR-PCSS).

Approximately 60 subjects will be enrolled, 30 with 2 eligible buttocks (to be dosed in the buttocks) and 30 with 2 eligible thighs (to be dosed in the thighs) at approximately 5 sites in the United States. No subjects will be treated for EFP in both the buttocks and the thighs. The 30 subjects in each treatment region (buttocks or thighs) will be assigned to 1 of 5 injection technique treatment arms on Day 1.

Subjects will participate in the study for approximately 92 days. Following a screening period of up to 21 days, subjects will participate in up to 3 treatment visits separated by 21 days (Days 1, 22, and 43). Following the first dose of study drug, subjects will return for assessments on Days 4, 8, 15, 22, 43 and 71.

The complete schedule of events is provided in Section 5.

10.2. Selection of Doses

The dosage of CCH chosen for this study is based on the experience from several earlier studies as well as ongoing Phase 3 clinical studies. The dose of 1.68 mg (0.84 mg per region) has been shown to be safe and well-tolerated.

10.3. Study Drug Administration

There are 5 treatment arms per region (buttocks or thigh) in this study with each arm representing a different injection technique as follows:

- Treatment I: Shallow Injection, 3 aliquots.
- Treatment II: Shallow injection, 1 aliquot.
- Treatment III: Deep injection, 1 aliquot.
- Treatment IV: Deep and shallow injections, 5 aliquots.
- Treatment V: Shallow injection, 4 aliquots.

Injection techniques differ from each other in, at least but not limited to, concentration of the CCH injectate, angle of injection, depth of injection, volume of injection and study drug administration at injection site.

Across all treatment arms, study drug will be administered subcutaneously while the subject is in a prone position. Each subject will receive 24 injections for a total dose of 1.68 mg (0.84 mg per treatment region) at each treatment visit. The cumulative CCH dose will be 5.04 mg for each subject that completes the 3 treatment visits.

The injection volume and concentration for each treatment arm are outlined in [Table 1](#).

Table 1: Volume and Concentration of CCH Injections by Treatment Arm

[figure not shown]
Treatment	Number of subjects/area	Dose/ injection	Volume/injection	Drug concentration/injection	Total volume/treatment visit
Treatment I: Shallow Injection, 3 aliquots	6 (buttocks) 6 (thighs)	0.07 mg	0.3 mL (given as 3- 0.1 mL aliquots)	0.23 mg/mL	7.2 mL (12 injections/ treatment area x 2 treatment areas x 0.3 mL)
Treatment II: Shallow injection, 1 aliquot	6 (buttocks) 6 (thighs)	0.07 mg	0.3 mL (given as 1- 0.3 mL aliquot)	0.23 mg/mL	7.2 mL (12 injections/ treatment area x 2 treatment areas x 0.3 mL)
Treatment III: Deep injection, 1 aliquot	6 (buttocks) 6 (thighs)	0.07 mg	0.3 mL (given as 1- 0.3 mL aliquot)	0.23 mg/mL	7.2 mL (12 injections/ treatment area x 2 treatment areas x 0.3 mL)
Treatment IV: Deep and shallow injections, 5 aliquots	6 (buttocks) 6 (thighs)	0.07 mg	1.5 mL (given as 5- 0.3 mL aliquots)	0.047 mg/mL	36 mL (12 injections/ treatment area x 2 treatment areas x 1.5 mL)
Treatment V: Shallow injection, 4 aliquots	6 (buttocks) 6 (thighs)	0.07 mg	1.2 mL (given as 4- 0.3 mL aliquots)	0.060 mg/mL	28.8 mL (12 injections/ treatment area x 2 treatment areas x 1.2 mL)

10.3.1. Treatment I: Shallow Injection, 3 Aliquots

In Treatment I, study drug will be injected subcutaneously using a 1 mL syringe with 0.1 mL gradients and a 30-gauge ½-inch needle, while the subject lies in a prone position. Each injection will consist of a single skin injection of study drug administered as three 0.1 mL aliquots to Positions A, B, and C (for a total injection volume of 0.3 mL) as shown in Figure 1. The depth of injection corresponds to the length of the treatment needle (1/2 inch) from the tip of needle to the hub or base of needle without downward pressure.

During each treatment visit, 8 syringes (4 syringes per treatment area) will be prepared for dosing. Each syringe will contain 0.9 mL of study drug (3 injections in each syringe).

Figure 1: Treatment I: Shallow Injection, 3 Aliquots

- With the needle positioned perpendicular to skin surface and perpendicular to the long axis of a dimple if the dimple is an elongated trough-like dimple (Position A), push the needle all the way in (1/2 inch) and inject 0.1 mL of study drug by gently pushing the syringe plunger. In most cases, the plane containing injection points A, B, and C will be parallel to the long axis of the subject's body.
- Withdraw the needle slightly and reposition it at an angle of approximately 45° to the skin surface and towards the subject's head (Position B), push the needle all way in and inject 0.1 mL of study drug by gently pushing the syringe plunger. Position B should always be towards the head of the subject.
- Withdraw the needle slightly and reposition it at an angle of approximately 45° to the skin surface and towards the subject's feet (Position C), push the needle all the way in and inject 0.1 mL of study drug by gently pushing the syringe plunger. Position C should always be towards the feet of the subject.
- Withdraw the needle completely from the injection site and proceed to next injection site.
- A syringe with 0.9 mL study drug will be sufficient for 3 injection sites.

[figure not shown]
- Use four (4) 0.9 mL syringes in each treatment area (each buttock or each thigh) to administer a total of 12 injections of 0.3 mL (3 aliquots of 0.1 mL each) at 12 injection sites.
- Discard the used needles and syringes.
- A total of 24 injections will be administered across the 2 treatment areas (2 buttocks or 2 thighs) at each treatment visit.

10.3.2. Treatment II: Shallow Injection, 1 Aliquot

In Treatment II, study drug will be injected subcutaneously using a 1 mL syringe with 0.1 mL gradients and a 30-gauge ½-inch needle while the subject is in a prone position. Each injection will consist of a single skin injection of study drug administered as a single shallow injection of a 0.3 mL aliquot as shown in Figure 2. The depth of injection corresponds to the length of the treatment needle (1/2 inch) from the tip of needle to the hub or base of needle without downward pressure.

During each treatment visit, 8 syringes (4 syringes per treatment area) will be prepared for dosing. Each syringe will contain 0.9 mL of study drug (3 injections in each syringe).

Figure 2: Treatment II, Shallow Injection, 1 Aliquot

- With the needle positioned at approximately 30° to the skin surface at the injection site and directed towards subject's head, push the needle all the way in (1/2 inch) and inject 0.3 mL of study drug by gently pushing the syringe plunger.
- Withdraw the needle completely from the injection site and proceed to the next injection site.
- A syringe with 0.9 mL study drug will be sufficient for 3 injection sites.
- Use four (4) 0.9 mL syringes for each treatment area (each buttock or each thigh) to administer a total of 12 injections of 0.3 mL (3 aliquots of 0.1 mL each) at 12 injection sites.

[figure not shown]
- Discard the used needles and syringes.
- A total of 24 injections will be administered across the 2 treatment areas (2 buttocks or 2 thighs) at each treatment visit.

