10.3.3. Treatment III: Deep Injection, 1 Aliquot

In Treatment III, study drug will be injected subcutaneously using a 1 mL syringe with 0.1 mL gradients and a 30-gauge 1-inch needle, while the subject is in a prone position. Each injection will consist of a single skin injection of study drug administered as a single deep injection of a 0.3 mL study drug aliquot as shown in Figure 3. The depth of injection corresponds to the length of the treatment needle (1 inch) from the tip of needle to the hub or base of needle without downward pressure.

During each treatment visit, 8 syringes (4 syringes per treatment area) will be prepared for dosing. Each syringe will contain 0.9 mL of study drug (3 injections in each syringe).

Figure 3: Treatment III: Deep Injection, 1 Aliquot

- With the needle positioned at an angle of approximately 30° to the skin surface at the injection site and directed towards subject's head, push the needle all the way in (1 inch) and inject a single aliquot 0.3 mL of study drug by gently pushing the syringe plunger.
- Withdraw the needle completely from the injection site and proceed to the next injection site.
- A syringe with 0.9 mL study drug will be sufficient for 3 injection sites.
- Use four (4) 0.9 mL syringes in each treatment area (each buttock or each thigh) to administer a total of 12 injections of 0.3 mL (single 0.3 mL aliquots) at 12 injection sites.
- Discard the used needles and syringes.

[figure not shown]
- A total of 24 injections will be administered across 2 treatment areas (2 buttocks or 2 thighs) at each treatment visit.

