10.3.5. Treatment V: Shallow Injections, 4 Aliquots

Study drug will be injected subcutaneously using a 3 mL syringe with 0.1 mL gradients and a 30-gauge ½ -inch needle, while the subject lies in a prone position. Each injection will receive a single skin injection of study drug administered as four 0.3 mL aliquots to Position A, B, C and D (for a total injection volume of 1.2 mL) as shown in Figure 5. The depth of injection corresponds to the length of the treatment needle (1/2 inch) from the tip of the needle to the hub or base of the needle without downward pressure.

During each treatment visit, 24 syringes (12 syringes per treatment area) will be prepared for dosing. Each syringe will contain 1.2 mL of study drug (4 aliquots of 0.3 mL each).

Figure 5: Treatment V: Shallow Injections, 4 Aliquots

- With the needle positioned at an angle of approximately 30° to skin surface at the injection site and directed towards one side of the subject, push the needle all the way in (1/2 inch), and inject 0.3 mL of study drug by gently pushing the syringe plunger.

- Maintain the 30° angle of the needle to the skin surface, reposition the needle to approximately 60° from Position A and towards the subject's shoulder (Position B), and inject 0.3 mL of study drug by gently pushing the syringe plunger.
- Maintain the 30° angle of the needle to the skin surface, reposition the needle to approximately 60° from Position B and towards subjects other shoulder (Position C) and inject 0.3 mL of study drug by gently pushing the syringe plunger.
- Maintain the 30° angle of the needle to the skin surface, reposition the needle opposite to position A and towards other side of the subject (Position D) and inject 0.3 mL of study drug by gently pushing the syringe plunger.
- A 3 mL syringe with 1.2 mL of study drug will be sufficient for one injection site.
- Use twelve (12) 3 mL syringes (with 1.2 mL study drug in each) in each treatment area (each buttock or each thigh) to administer a total of 12 injections of 1.2 mL each (total of 14.4 mL, 4 aliquots of 0.3 mL each) at 12 injection sites.
- Discard the used needle and syringes.
- A total of 24 injections will be administered across 2 treatment areas.

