**Table 2: Volume and Concentration of Injections**

Treatment	Number of Subjects/Area	Dose/ Injection	Volume/Injection	Drug Concentration/ Injection	Total Volume/ Treatment Visit
Treatment I: Shallow injection, 3 aliquots	6 (buttocks) 6 (thighs)	0.07 mg	0.3 mL (given as 3 - 0.1 mL aliquots)	0.23 mg/mL	7.2 mL (12 injections/ treatment area x 2 treatment areas x 0.3 mL)
Treatment II: Shallow injection, 1 aliquot	6 (buttocks) 6 (thighs)	0.07 mg	0.3 mL (given as 1 - 0.3 mL aliquot)	0.23 mg/mL	7.2 mL (12 injections/ treatment area x 2 treatment areas x 0.3 mL)
Treatment III: Deep injection, 1 aliquot	6 (buttocks) 6 (thighs)	0.07 mg	0.3 mL(given as 1 - 0.3 mL aliquot)	0.23 mg/mL	7.2 mL (12 injections/ treatment area x 2 treatment areas x 0.3 mL)
Treatment IV: Deep and shallow injections, 5 aliquots	6 (buttocks) 6 (thighs)	0.07 mg	1.5 mL (given as 5 - 0.3 aliquots)	0.047 mg/mL	36 mL (12 injections/ treatment area x 2 treatment areas x 1.5 mL)
Treatment V: Shallow injection, 4 aliquots	6 (buttocks) 6 (thighs)	0.07 mg	1.2 mL (given as 4 - 0.3 mL aliquots)	0.060 mg/mL	28.8 mL (12 injections/ treatment area x 2 treatment areas x 1.2 mL)

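### Two dosing statements are wrong as written: the Treatment II syringe step gives Treatment I's three 0.1 mL aliquots, and Treatment V's 0.060 mg/mL should be 0.058 mg/mL

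*Protocol*

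**What the plan says.** **Treatment II.** The narrative of Protocol 10.3.2 has each injection "administered as a single shallow injection of a 0.3 mL aliquot as shown in Figure 2". The injection step tells the operator to "push the needle all the way in (1/2 inch) and inject 0.3 mL of study drug by gently pushing the syringe plunger" and then to withdraw fully. Protocol Table 1 agrees ("0.3 mL (given as 1- 0.3 mL aliquot"), as does SAP Table 2 ("0.3 mL (given as 1 - 0.3 mL aliquot"). The later step in 10.3.2 on how many syringes to use instead describes "a total of 12 injections of 0.3 mL (3 aliquots of 0.1 mL each) at 12 injection sites".

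**Treatment V.** Protocol Table 1 and SAP Table 2 give the same row: 0.07 mg per injection, 1.2 mL per injection, concentration 0.060 mg/mL, total volume 28.8 mL per visit. Protocol 10.3.5 confirms the volume: "Each syringe will contain 1.2 mL of study drug (4 aliquots of 0.3 mL each". Protocol 10.3 and SAP 3.6 give every arm 24 injections and 1.68 mg per visit. SAP 3.6 adds that each treatment area receives 0.84 mg whichever technique is assigned.

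**The concern.** The primary objective is to assess the effects of CCH under different injection techniques, so the technique and concentration entries define the treatments. Arms I and II share dose, volume, concentration, syringe and needle. They differ only in how the 0.3 mL is delivered: number of aliquots, needle angle and deposit positions. The stray phrase falls on one of those few features. A site that followed it would remove the aliquot-count difference between the two arms.

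For Treatment V, a concentration that disagrees with its own dose and volume leaves the reader unsure which figure governs. If the concentration were used for preparation, the arm would exceed the common dose. Protocol 14.6.2.1 counts any amount above the protocol dose as an overdose to be recorded.

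**Working it through.** **Treatment II: the statements side by side**

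- Section heading, narrative and injection step of Protocol 10.3.2: one 0.3 mL aliquot, one placement at about 30 degrees.
- Arm list and Table 1 in Protocol 10.3, and SAP Table 2: one 0.3 mL aliquot.
- Syringe-use step of 10.3.2: three 0.1 mL aliquots.
- Same step for Treatment I (10.3.1): "12 injections of 0.3 mL (3 aliquots of 0.1 mL each) at 12 injection sites". The parenthetical is identical.
- Same step for Treatment III (10.3.3), the other one-aliquot arm: "a total of 12 injections of 0.3 mL (single 0.3 mL aliquots) at 12 injection sites".

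The phrase matches the three-aliquot arm and conflicts with every other description of Treatment II, which points to text carried over from 10.3.1. The sentence is complete and grammatical, so text extraction does not explain it. Volume is unaffected: 3 × 0.1 mL = 1 × 0.3 mL = 0.3 mL. The arm has 6 buttock and 6 thigh subjects, 12 of the 60 planned.

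**Treatment V: concentration = dose / volume**

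The stated dose totals reproduce: 12 × 0.07 = 0.84 mg per area, 24 × 0.07 = 1.68 mg per visit, 3 × 1.68 = 5.04 mg cumulative. Doses and volumes below are from Protocol Table 1. The last three columns take the concentration in the fourth column literally.

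| Arm | Volume (mL) | 0.07 / volume (mg/mL) | Concentration (mg/mL) | mg per injection | mg per visit (× 24) | Difference from stated dose |
|---|---|---|---|---|---|---|
| I, II, III | 0.3 | 0.2333 | 0.23 (printed) | 0.0690 | 1.656 | −1.4% |
| IV | 1.5 | 0.0467 | 0.047 (printed) | 0.0705 | 1.692 | +0.7% |
| V | 1.2 | 0.0583 | 0.060 (printed) | 0.0720 | 1.728 | +2.9% |
| V, corrected | 1.2 | 0.0583 | 0.058 | 0.0696 | 1.670 | −0.6% |

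The visit totals give the same concentration for V: 1.68/28.8 = 0.0583 mg/mL.

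To see whether rounding explains each row, take the range of true concentrations that would round to the printed value and multiply by the volume:

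- I to III: 0.225 to 0.235 × 0.3 = 0.0675 to 0.0705 mg, which includes 0.07.
- IV: 0.0465 to 0.0475 × 1.5 = 0.06975 to 0.07125 mg, which includes 0.07.
- V: 0.0595 to 0.0605 × 1.2 = 0.0714 to 0.0726 mg, which excludes 0.07.

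Only row V fails. The syringe fill confirms its volume and the visit total confirms its dose, so the concentration is the wrong figure. Taken literally, it gives 12 × 0.072 = 0.864 mg per area and 3 × 1.728 = 5.184 mg cumulative.

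The concentration contrast between arms barely changes. Arms I to III against V is 0.23/0.060 = 3.8-fold as printed and 0.2333/0.0583 = 4.0-fold from dose and volume. V against IV is 0.060/0.047 = 1.28 as printed and 0.0583/0.0467 = 1.25 from dose and volume.

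**The case against.** The strongest reply is that neither slip is likely to change what is done to a subject.

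The Treatment II intent is plain on the same page. The step that directs the injection gives one placement and one push, and no second or third position is described, so a site could not carry out Treatment I's three-position delivery from this section. Three 0.1 mL pushes through an unmoved needle would still deposit 0.3 mL in one place. This stands: the technique contrast with Treatment I would be blurred at most, and 12 subjects is the size of the arm, not of an effect.

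For Treatment V, 0.0583 does round to 0.06 at two decimals, so the printed figure is probably that value with a zero added. The dose is fixed elsewhere, and Protocol 18.4 sends sites to separate Reconstitution Instructions. The gap is 0.002 mg per injection. The syringe has 0.1 mL graduations; assuming a reading error of half a graduation, 0.05/1.2 = 4.2% would exceed the 2.9% at issue. This also stands as an argument about size. It does not make the entry correct: the printed zero claims a third decimal, and row IV, directly above, is correctly rounded to three.

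That the intent can be recovered does not justify leaving a conflicting procedural step in place. Amendment 1 already corrected Figure 4 because its needle positions disagreed with the text, and the Treatment II step is the same kind of mismatch.

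**Conclusion.** Both statements are wrong as written, and the correct values are unambiguous. For Treatment II the error concerns delivery only: dose and volume do not change, and angle and deposit points still distinguish it from Treatment I. For Treatment V the printed concentration is 2.9% above the value implied by the row's own dose and volume. An excess of 0.048 mg per visit (1.728 − 1.68) would follow only if preparation used the printed figure. That is an assumption the documents cannot settle, and nothing in them shows that any subject was misdosed. These are minor corrections to dosing text that should be made. They are not design flaws.

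**What to change.** - In the syringe-use step of Protocol 10.3.2, replace the three-aliquot parenthetical with the one used for Treatment III in 10.3.3, a single 0.3 mL aliquot.
- In the Treatment V row of Protocol Table 1 and SAP Table 2, change 0.060 mg/mL to 0.058 mg/mL.
- Confirm that the Reconstitution Instructions deliver 0.07 mg in 1.2 mL for Treatment V.
- Optionally, in the Protocol synopsis and in 10.2 and 10.3, attach the 0.84 mg to the treatment area and not the region, as SAP 3.6 does. SAP 3.4 uses region for the buttocks or thighs as a whole.

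The required changes are one phrase, one cell in each of two tables, and one check of a supporting document. Sample size, visits, endpoints and analysis stay as they are.

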10.3.3. Treatment III: Deep Injection, 1 Aliquot

In Treatment III, study drug will be injected subcutaneously using a 1 mL syringe with 0.1 mL gradients and a 30-gauge 1-inch needle, while the subject is in a prone position. Each injection will consist of a single skin injection of study drug administered as a single deep injection of a 0.3 mL study drug aliquot as shown in Figure 3. The depth of injection corresponds to the length of the treatment needle (1 inch) from the tip of needle to the hub or base of needle without downward pressure.

During each treatment visit, 8 syringes (4 syringes per treatment area) will be prepared for dosing. Each syringe will contain 0.9 mL of study drug (3 injections in each syringe).

Figure 3: Treatment III: Deep Injection, 1 Aliquot

- With the needle positioned at an angle of approximately 30° to the skin surface at the injection site and directed towards subject's head, push the needle all the way in (1 inch) and inject a single aliquot 0.3 mL of study drug by gently pushing the syringe plunger.
- Withdraw the needle completely from the injection site and proceed to the next injection site.
- A syringe with 0.9 mL study drug will be sufficient for 3 injection sites.
- Use four (4) 0.9 mL syringes in each treatment area (each buttock or each thigh) to administer a total of 12 injections of 0.3 mL (single 0.3 mL aliquots) at 12 injection sites.
- Discard the used needles and syringes.

[figure not shown]
- A total of 24 injections will be administered across 2 treatment areas (2 buttocks or 2 thighs) at each treatment visit.

